6.1.5.6 Clinical Outcome Assessment

Subjects must meet the following to be included in the CE populations:

- For the CE-EOT population:
 - Completed the investigator's assessment of clinical response (ie, was not deemed an indeterminate outcome) at the EOT visit, and
 - The EOT visit occurred on the day of, or within 2 days following the last dose of test article.
- For the CE-PTE population:
 - The overall Clinical Response (based on the investigator's assessment) at the PTE Visit is not Indeterminate.
 - The PTE Visit occurred 7 to 14 days after the last dose of test article, unless the subject was considered to be a Clinical Failure based on the investigator's assessment at the EOT visit.

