5.2.2.1.2 PTE Visit

At the PTE Visit (7 to 14 days after the subject's last day of study therapy) the investigator will indicate one of the following outcomes relating to the primary infection under study:

Clinical Success at the Post Therapy Evaluation assessment will be defined as meeting the following:

- The subject is alive
- The infection is sufficiently resolved such that further antibacterial therapy is not needed. These subjects may have some residual changes related to infection requiring ancillary (ie, non-antibiotic) treatment, eg, bandages on a healing wound, debridement of uninfected tissue (ie, necrotic)

Clinical Failure will be defined as meeting any of the criteria below:

- The infection required additional treatment with alternative (rescue) antibacterial therapy
- The subject received antibacterial therapy between EOT and PTE that may be effective for the infection under study for a different infection from the one under study
- Unplanned major surgical intervention (ie, procedures that would not normally be performed at the bedside) for the infection under study between EOT and PTE
- The subject died before evaluation
- Other specified reason

Indeterminate The clinical response to test article could not be adequately inferred:

- The subject was not seen for PTE assessment because they withdrew consent, were lost to follow-up, or other specified reason
- Other specified reason

Overall Clinical Response at PTE (based on the investigator's assessment) is determined as follows ([Table 2](#)) from the investigator's assessments at the EOT and PTE Visits:

Table 2. Investigator's Assessment of Clinical Response

EOT Visit	PTE Visit	Overall Assessment of Clinical Response at PTE Visit
Success	Success	Success
Success	Failure	Failure
Success	Indeterminate	Indeterminate
Failure	Success	Failure
Failure	Failure	Failure
Failure	Indeterminate	Failure
Indeterminate	Success	Indeterminate
Indeterminate	Failure	Failure
Indeterminate	Indeterminate	Indeterminate

EOT = end of treatment; PTE = post-therapy evaluation.

For the mITT population, the proportion of mITT subjects with a Clinical Success is defined using the following formula (where the denominator adds to the total number of subjects in the mITT population):

$$\frac{\text{Number of subjects with Clinical Success}}{(\text{Number of subjects with Clinical Success} + \text{Number of subjects with a Clinical Failure} + \text{Number of subjects with an Indeterminate response})}$$

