6.1.5.5 Test Article Therapy

Subjects must meet all of the following to be included in the CE populations:

- Received test article and the correct test article based on the randomization assignment
- Study personnel involved in the assessment of efficacy remained blinded to study treatment, unless a treatment limiting adverse event occurred which required emergency unblinding.
- Subject was at least 80% compliant with the dosing regimen.
- Evaluable failure: The subject received at least 2 doses of active test article (omadacycline group) or at least 4 doses of active test article (linezolid group) and the investigator classifies the subject as a Clinical Failure at the EOT Visit (CE-EOT population) or the overall Clinical Response (based on the investigator's assessment) at the PTE Visit (CE-PTE population) is Clinical Failure.
- Evaluable success: The subject received at least 3 doses of active test article (omadacycline group) or at least 6 doses of active test article (linezolid group) and the investigator classifies the subject as a Clinical Success at the EOT Visit (CE-EOT population) or the overall Clinical Response (based on the investigator's assessment) at the PTE Visit (CE-PTE population) is Clinical Success.

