8.6 Visit Windows/Unscheduled Visits

For the primary efficacy outcome, if more than one assessment of the lesion size is done in the 46-72 hour window, the latest will be used. For secondary and additional efficacy outcomes, the data collected at the EOT and PTE Visits, regardless of when these occur will be utilized in the analysis in the mITT population. The CE and ME populations exclude subjects with a visit occurring outside the window allowed per protocol.

For each safety outcome, analyses will utilize assessments occurring during the scheduled visit windows (provided in [Table 7](#)). Thus, if a subject has a visit outside the scheduled visit window, for example, a PTE Visit occurred 20 days after the subject's last day of therapy, the assessment will not be summarized with the PTE Visit but will be considered an unscheduled assessment. If a subject does not have an assessment at a scheduled visit and an unscheduled assessment was taken within the window for the time point (for example, 7 to 14 days after the subject's last day of therapy for PTE), these assessments will be summarized in the by time point analyses. If more than one measurement is taken during the visit window, the value taken on the scheduled visit will be utilized or if no scheduled visit was done, the first (earliest) measurement in the visit window will be used. If more than one measurement is taken on the same day, the assessment closest to the start of the dose will be used for on treatment values and the last measurement on the day will be used for post-treatment values. For worst overall post-baseline analyses, all assessments including those obtained from unscheduled visits will be included.

Table 7. Scheduled Study Visits

Study Visit	Study Day	Notes
Baseline	Day -1 or Day 1	Except where indicated, last measurement prior to the first dose of test article. Screening assessments are to be taken within 24 hours prior to the first dose of test article. If no test article is taken, the date and time of randomization is used in place of the first dose of test article.
On Treatment (note: analysis visit will be each Study Day)	Day 1, Day 2, Day 3, Day 7, Day 10	The Day 3 visit is to occur within 46 to 72 hours after the first dose of study drug and thus, may occur on Study Day 4. A Day 10 visit is will be conducted for subjects with treatment extending beyond 9 days, unless this visit coincides with the EOT Visit.
EOT		Within 2 days following the last dose of test article

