9 STATISTICAL ANALYSIS METHODS

9.1 Subject Disposition

The number of Screen Failures and reason for screen failure will be presented overall. A listing, grouped by stratum, will be provided that indicates the subject's date and time of randomization, randomized treatment assignment, randomization number, kit number(s), block number, randomized infection type, and prior antibiotic stratum (receipt of an allowed antibacterial therapy in the 72 hours prior to randomization - yes or no).

The number of subjects included in each of the analysis populations (ie, ITT, Safety, mITT, micro-mITT, CE-EOT, CE-PTE, ME-EOT and ME-PTE) will be summarized by treatment group. A table will summarize the reasons for exclusion from each population and a listing will be provided that indicates each subject's inclusion in/exclusion from the populations and the reason for exclusion from each of the populations.

A listing will be provided of randomized subjects who did not meet all inclusion/exclusion criteria, and which criteria were not met. The number and percentage of subjects completing the study (defined as receiving at least one dose of test article and returning for all of the EOT, PTE and FU visits), not completing the study, missing each of the EOT and PTE Visits, and prematurely discontinuing from test article will be presented for each treatment group and overall for the ITT, mITT, and CE-PTE populations (by definition, a subject in the CE-PTE population cannot have missed the PTE Visit, unless the subject was a clinical failure at the EOT Visit). Reasons for premature discontinuation of test article, not completing the study, and for missing each of the visits, as recorded on the eCRF will be summarized (number and percentage) by treatment group. Percentages of subjects discontinued from test article and not completing the study will be compared between treatment groups using Fisher's exact test. A listing of all subjects who prematurely discontinued from test article or not completing the study will be presented, and the primary reason for discontinuation of test article or not completing the study will be provided.

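### The CE-PTE visit-window rule exempts only failures at EOT, so a subject who fails after EOT is dropped if they die before the PTE visit or have it less than 7 days after the last dose

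*SAP*

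**What the plan says.** SAP 6.1.5.6 sets the timing condition for CE-PTE: "The PTE Visit occurred 7 to 14 days after the last dose of test article, unless the subject was considered to be a Clinical Failure". The exemption is limited to a subject "considered to be a Clinical Failure based on the investigator's assessment at the EOT visit".

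Two other sections agree with this reading. SAP 8.6 states that "The CE and ME populations exclude subjects with a visit occurring outside the window allowed per protocol", with no exemption for failures. SAP 9.1 says that "a subject in the CE-PTE population cannot have missed the PTE Visit, unless the subject was a clinical failure at the EOT Visit".

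Other parts of the SAP treat failure after EOT as a full outcome:

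- SAP 5.2.2.1.2 lists among the failure criteria at PTE "The infection required additional treatment with alternative (rescue) antibacterial therapy" and "The subject died before evaluation".
- SAP Table 2 maps EOT Success with PTE Failure, and EOT Indeterminate with PTE Failure, to an overall Failure.
- SAP 6.1.5.5 counts a sufficiently dosed subject as an evaluable failure when "the overall Clinical Response (based on the investigator's assessment) at the PTE Visit (CE-PTE population) is Clinical Failure".
- SAP 6.1.5.3 does not exclude a subject whose concomitant antibiotic was given because test article did not work well enough.
- SAP 6.1.5.4 keeps subjects with unplanned major surgery for the infection by deeming them failures at both EOT and PTE.

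For mITT, SAP 8.6 says EOT and PTE data "regardless of when these occur will be utilized in the analysis in the mITT population".

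**The concern.** A lower limit on visit timing guards against declaring success too soon, because a subject who looks well a few days after therapy may still relapse. It does not serve that purpose for a failure. Once a subject has died, or has needed rescue and been recorded as a failure at the PTE visit, Table 2 offers no route back to success.

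The rule therefore removes some failures whose outcome is settled and removes them because of events tied to that outcome. Death prevents an in-window visit, and a relapse can prompt an early one. The CE-PTE success rate is raised as a result. If such failures are more frequent in one arm, the CE-PTE difference is tilted in favour of that arm.

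The SAP also treats similar failures differently. A failure through unplanned major surgery is kept whatever its timing. A failure through rescue antibacterial therapy or death may not be.

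**Working it through.** **Step 1. Apply the rules to each kind of subject.** All subjects below are assumed to meet every other CE criterion.

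| Course | Overall response (Table 2) | In CE-PTE? |
|---|---|---|
| Failure at EOT, PTE visit at any time or missed | Failure | Yes, exempt (6.1.5.6) |
| Success at EOT, rescued, PTE visit 7 to 14 days after last dose | Failure | Yes, in window |
| Unplanned major surgery for the infection | Failure | Yes, deemed failure at EOT (6.1.5.4) |
| Success or Indeterminate at EOT, dies before PTE visit | Failure | **No**, no visit in window |
| Success or Indeterminate at EOT, failure recorded at a PTE visit before 7 days | Failure | **No**, visit too early |
| Success at EOT, PTE missing | Indeterminate | No, for a different reason |

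The gap is the fourth and fifth rows. In mITT the same subjects count as failures. ME-PTE inherits the loss because SAP 6.1.6 builds it from CE-PTE.

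**Step 2. Reproduce the plan's figure for this population.** Inputs from SAP 5.1.1 and Table 1: 564 CE subjects, hence 282 per arm at 1:1; 90% success in both arms; margin 10%; one-sided alpha 0.025.

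- Farrington-Manning restricted estimates under a difference of -0.10: 0.8313 and 0.9313.
- Null SE = √[(0.8313×0.1687 + 0.9313×0.0687)/282] = 0.0269.
- Alternative SE = √[2×0.9×0.1/282] = 0.0253.
- Power = Φ[(0.10 − 1.96×0.0269)/0.0253] = 96.9%.

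The SAP states 97%, so the figure reproduces. The concern is about a population rule and does not dispute it.

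**Step 3. Illustrate the size.** The documents do not say how many subjects fall in the gap, so the counts here are assumptions. The base is 254/282 = 90.1% per arm, which leaves 282 − 254 = 28 failures. Returning k failures to an arm gives a rate of 254/(282 + k). The limit is the lower end of the unstratified Miettinen-Nurminen 95% interval, as in SAP 10.3.

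| Returned (omadacycline, linezolid) | Rates | Difference (points) | Lower limit (points) |
|---|---|---|---|
| 0, 0 | 90.1%, 90.1% | 0 | -5.0 |
| 3, 3 | 89.1%, 89.1% | 0 | -5.2 |
| 8, 8 | 87.6%, 87.6% | 0 | -5.4 |
| 6, 2 | 88.2%, 89.4% | -1.2 | -6.5 |
| 6, 0 | 88.2%, 90.1% | -1.9 | -7.1 |

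Even a one-sided loss of 6 failures leaves the limit inside -10.

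**Step 4. Judge the assumed range.** Returning 3 to 8 failures means that 3/31 = 10% to 8/36 = 22% of an arm's evaluable failures fall in the gap. Nothing in the documents supports a share that large, so the upper rows are best read as bounds for illustration.

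**The case against.** The strongest reply is that few subjects are affected and little rests on them. Most of it stands.

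*A relapser is usually kept.* A reader might infer that anyone rescued between EOT and PTE is lost. The documents do not support that. The PTE visit is scheduled 7 to 14 days after last therapy, and nothing tells sites to bring it forward on relapse. The failure criteria look back over the interval since EOT. A subject rescued on the fourth day after therapy who attends on the tenth is an in-window failure, and SAP 6.1.5.3 does not exclude the rescue. Only a relapse contact entered as an early PTE visit falls in the gap.

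*Late visits differ.* A reader might extend the point to every out-of-window visit. A failure first recorded more than 14 days after the last dose may have arisen after the window, and excluding it can be legitimate. Whether it did depends on the date of the event, not of the visit.

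*No conclusion hangs on CE-PTE here.* A reader might infer a bias toward declaring non-inferiority. In this SAP the primary analysis is Early Clinical Response in mITT, and SAP 10.3 makes the PTE intervals descriptive with no non-inferiority conclusion. The mITT analysis at PTE keeps these subjects.

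The text of the rule survives the reply. Deaths between EOT and PTE are failures by definition and cannot yield a visit in the window, whatever the sites' scheduling habits. No other section brings those subjects, or failures at an early PTE visit, back in.

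**Conclusion.** The concern holds in a narrow form. As written, SAP 6.1.5.6 drops from CE-PTE and ME-PTE a subject who becomes an overall Clinical Failure after EOT and who either dies before the PTE visit or has the failing PTE visit less than 7 days after the last dose. This sits badly with SAP Table 2, 6.1.5.5 and 6.1.5.4, which treat such outcomes as evaluable failures or protect comparable ones.

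The certain effect of each such exclusion is a higher CE-PTE success rate. A biased treatment difference requires imbalance between arms, which the documents neither show nor suggest. Under the assumed counts, balanced losses change the lower limit by at most 0.4 points and a 6-versus-0 split by about 2 points. Neither reaches the margin.

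In this FDA SAP the consequence is confined to a descriptive secondary summary. It would be larger if the separate EMA SAP, which was not available, uses the same wording. Protocol 22.4.3 makes CE co-primary for the EMA and requires non-inferiority in both mITT and CE. Severity is low, and this is a cheap improvement.

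**What to change.** In SAP 6.1.5.6, extend the exemption to a second group: subjects whose overall Clinical Response at PTE is Clinical Failure and whose failure event is dated on or before 14 days after the last dose of test article. The failure event is the start of rescue antibacterial therapy, death, or another listed failure criterion. Tying the exemption to the event date admits early failures and deaths, and it handles late visits correctly. All other CE criteria stay in force.

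Amend SAP 8.6 and 9.1 to match, since both would otherwise contradict the new text. ME-PTE follows through SAP 6.1.6. Check the EMA SAP for the same rule. Make the change before database lock, while classification is still blinded.

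The cost is a few lines in three sections plus one derivation. Table 2 carries no failure date, so one must be built from data such as rescue antibacterial start dates and death dates. A few more failures will enter CE-PTE and lower its success rates slightly. The primary analysis is untouched. A subject with no PTE assessment who is Indeterminate under Table 2 would still be excluded.

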6.1.5.7 Baseline Medical Events

Subjects will be excluded from the CE populations if the investigator has documented in the eCRF that they meet any one of the following protocol-defined exclusion criteria at baseline (ie, prior to randomization):

Exclusion Criterion 3: Infections where the outcome is strongly influenced by factors other than protocol-defined treatment and procedures, that require antibacterial treatment for greater than 14 days, are associated with chronic skin lesions that may obscure determination of response even after successful bacterial eradication has been achieved, or are suspected or known to be caused by a pathogen resistant to either test article, eg:

- Chronic (persistently present greater than 3 months) lesions, ulcers or wounds (eg, cellulitis contiguous with a diabetic foot ulcer)
- association with chronic dermatitis or any other chronic inflammatory skin lesion (eg, psoriasis, eczema)
- burns
- peri-rectal abscess (eg, buttock or perineal lesion likely to communicate with the rectum) or perineal infection
- infected decubitus (pressure) ulcers
- necrotizing fasciitis (infections with rapidly progressive destruction of tissue at or below the fascia)
- life-threatening infections, ie, require emergency surgery for the treatment (eg, progressive gangrene)
- infections in an area requiring surgery that in and of itself would cure the infection or remove the infected site (eg, amputation for vascular insufficiency)

- infections associated with severe vascular insufficiency (eg, peripheral vascular disease) or acute occlusion expected to require immediate revascularization
- infections associated with acute compartment syndrome expected to require extensive surgery to provide decompression
- infections accompanied by confirmed or suspected contiguous bone or joint infection (eg, osteomyelitis, septic arthritis, bursitis)
- bacteremic infections associated with an intravascular foreign body
- infections accompanied by another confirmed or suspected infection requiring systemic antibiotic therapy (eg, endocarditis, other endovascular infection, meningitis, visceral abscess, intra-abdominal infection, pneumonia, urinary tract infection)
- human or animal bites (infections associated with insect bites are NOT excluded)
- myonecrosis
- complicated by an immune deficiency in the subject (eg, ecthyma gangrenosum in a neutropenic subject)
- infections associated with the presence of a foreign body (eg, wood, metal, plastic, etc.) if the foreign body cannot be removed within 24 hours of first dose of test article

Exclusion 4: Inability to tolerate oral medication (eg, nausea, vomiting diarrhea or any other condition that might impair ingestion or absorption of oral medication)

Exclusion 19: Has been previously treated with omadacycline or previously enrolled in this study.

6.1.6 Microbiologically Evaluable (ME) Populations

The ME-EOT and ME-PTE populations will consist of all subjects in both the micro-mITT and the CE-EOT and CE-PTE populations, respectively.

6.2 Evaluability Review Team

6.2.1 Membership and Responsibilities

The Evaluability Review Team (ERT) will review both clinical and microbiological data for determination of criteria used to assess inclusion in the analysis populations and for determination of baseline and post-baseline pathogens. ERT members will be blinded to treatment assignment and will review the data concurrent with the conduct of the study. The ERT will be conducted in accordance with the ERT process documents.

6.2.2 Process for Determining Inclusion in Populations

Inclusion into the ITT and Safety populations will be determined programmatically from the eCRF data. Inclusion into the CE populations will be determined programmatically from the

eCRF data and the manual review conducted by the ERT. The ERT may review subject data to confirm that population criteria are satisfied.

Inclusion into the mITT and micro-mITT population will be determined programmatically by incorporating the outcome of the review of the isolates by the ERT. The ERT will determine whether each isolate (baseline and post-baseline) is considered a pathogen based on a review of information from baseline samples including infection type, type of specimen, and local and central laboratory genus and species identification. Inclusion into the ME populations will be determined programmatically.

Review of data, Sponsor determination of evaluability, and final subject population classification will be performed in a blinded manner prior to database lock and unblinding with the exception of those criteria requiring the subject's actual treatment assignment (for example, the requirement for the subject to have received the correct test article per the randomization assignment). For the criteria requiring the subject's actual treatment assignment, population determination will be completed programmatically after unblinding.

6.3 Subgroups

Analyses of Early Clinical Response and the overall assessment of Clinical Response at the PTE Visit (based on the investigator's assessment) will be conducted (as described in [Section 10.6](#)) for subgroups defined by the randomization stratification factors: infection type (cellulitis/erysipelas, wound infection and major abscess) and receipt of an allowed antibacterial therapy in the 72 hours prior to randomization (yes or no). Analyses of Early Clinical Response will also be conducted in the following subgroups: clinical site (sites that enroll less than 10 subjects per group will be grouped together), bacteremic subjects, subjects meeting the systemic inflammatory response syndrome (SIRS) criteria at baseline, size of lesion ($\leq 300 \text{ cm}^2$, > 300 to 600 cm^2 , > 600 to 1000 cm^2 , and $> 1000 \text{ cm}^2$), receipt of a nonsteroidal anti-inflammatory drug (NSAID) from the first dose of test article through to the assessment of Early Clinical Response, receipt of an operative incision and drainage (I&D) from the first dose of test article through to the assessment of Early Clinical Response and IV drug use vs no IV drug use. SIRS is defined as having 2 or more of the following criteria: temperature $< 36^\circ \text{ C}$ or $> 38^\circ \text{ C}$, heart rate > 90 bpm, respiratory rate > 20 bpm, or WBC count $< 4000 \text{ cells/mm}^3$ or $> 12,000 \text{ cells/mm}^3$ or $> 10\%$ bands.

Exploratory analyses in other subgroups may also be conducted.

